**Section 17. Health Service Use (3, 6, 9 and 12 months)**

17.1. Have you visited your GP since your stroke/TIA  Yes  No

17.1.1. If Yes, how often since your TIA/stroke?  Once  
 Twice  
 Three times  
 Four times  
 More than 4 times  
 Can't remember

17.2. Have you visited your GP since the last assessment  Yes  No

17.2.1. If Yes, how frequently have you visited your GP?  Once  
 Twice  
 Three times  
 Four times  
 More than 4 times  
 Can't remember/unknown

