### 3.5 CASE RECORD FORMS AND QUESTIONNAIRES

#### 20. LIST OF QUESTIONNAIRES

Table 1. List of outcome measures

Outcome measure	Baseline	3	6	12
Demographic Factors: Age, sex, ethnicity, employment, education, marital status	✓			
Event type - stroke and pathological subtypes, or TIA and event date (physician diagnosed)	✓			
Hospitalization details: hospital, date of admission, date of discharge	✓			
Event details (revascularization and planned procedures) from medical records	✓			
Hospital Anxiety and Depression Scale	✓	✓	✓	✓
Stroke awareness (recognition of risk factors, knowledge of actions) [61]	✓	✓	✓	✓
Quality of life (EQ-5D-5L) [62]	✓		✓	
Cognitive functioning by MoCA [63]	✓		✓	
Medication adherence and self-efficacy (SEAMS) REF)	✓	✓	✓	✓
Physical measurements (non-fasting blood test, SBP/DBP, BMI, HR)*	✓		✓	
Absolute and relative 5-year risk of stroke (as measured by Stroke Riskometer app)	✓		✓	
Lifestyle factors (Diet score, physical activity, smoking, alcohol)	✓	✓	✓	✓
CVD outcomes, recurrent events, hospitalisation (stroke, CVD events) self-report and/or from clinical records	✓	✓	✓	✓
Health and Service costs: NMDS (NZ)			✓	✓
Productivity level NMDS (NZ)	✓	✓	✓	✓
Participant feedback questionnaire – Intervention group only	✓	✓	✓	✓

Items will include demographic factors, medical history, lifestyle risk factors, awareness of stroke risk factors, warning signs, symptoms and actions;[64] depression screening test (Hospital Anxiety and Depression Scale) health related quality of life ([EQ-5D-5L](#)),[62] health-care resource

use questionnaire, cognitive assessment (Montreal Cognitive Assessment MoCA) and participant satisfaction questionnaires. See 2 for details of measures collected at each timepoint. Life's Simple 7 score will be calculated from corresponding measurements of smoking, BMI, physical activity, healthy diet score, blood total cholesterol, glucose level and BP.[37]

Table 2. Life's Simple 7

Modifiable factors	Poor health	Intermediate health	Ideal health
Smoking status	Current smoker	Former ≤ 12 months	Never or quit > 12 months
Body mass index	≥ 30 kg/m 	25–29.9 kg/m 	< 25 kg/m 
Physical activity	No physical activity	1–3 times, less than 2.5 hours per week	≥ 4 times per week, 2.5 hours or more
Healthy diet score	0–1 component	2–3 components	4–5 components
Total cholesterol	≥ 240 mg/dL	200–239 mg/dL or treated to goal	< 200 mg/dL

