## HEALTH ECONOMIC EVALUATION

The net costs and benefits of the intervention compared to the control will be described and reported in accordance with the Consolidated Health Economic Evaluation Reporting Guidelines (CHEERS). [97] For each intervention arm, the probability of resource use and associated costs will be reported. Cost estimates will be presented in terms of direct costs (e.g., healthcare), indirect costs (e.g. lost productivity) and out-of-pocket costs. Unit prices for resources utilised will be sourced from the most appropriate and up-to-date source (e.g., PHARMAC). Costs will be measured in actual prices for the reference year (e.g., 2023). Where prices in 2023 are unavailable, adjustment to the actual price will be made using the published health sector specific deflator/inflators. The overall 'Program Costs' (i.e., non-research related costs associated with providing the intervention) will be deducted from the potential cost-offsets from fewer readmissions or other resource savings. Sensitivity and uncertainty (probabilistic multivariable [Monte-Carlo simulated]) analyses to account for variability in point estimates will be performed to assess the robustness of results.

The analysis will include modelling the potential opportunity cost savings from future strokes averted based on changes in risk profile (e.g., change in absolute 5-year risk of stroke or clinically relevant change in LS7 score). An incremental cost/ quality-adjusted life year (QALY) gained will also be calculated. The EQ5D is the most commonly used in economic evaluations to estimate preference-based outcome measure and will be used to calculate QALYs for the cost utility analysis.[62, 98] Threshold and willingness-to-pay analyses, illustrated using cost effectiveness acceptability curves, will be performed to assess uncertainty in the model parameters or a range of different scenarios, to explore under what conditions HWC could be cost effective and yield potential cost offsets/savings. Potential savings will be calculated using a "case-averted" approach, which estimates the direct and indirect costs savings if the use of HWC leads to annual reduction in stroke incidence. These estimates will be extrapolated to the overall New Zealand population.

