17.14.1. If Yes to 17.14, what services?

---

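### The service-use form records no quantity for privately paid care, caps GP visits above four, and disagrees with Table 1 on timing, so it cannot fully supply the promised costs

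*Protocol*

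**What the plan says.** The Health Economic Evaluation section states: "Cost estimates will be presented in terms of direct costs (e.g., healthcare), indirect costs (e.g. lost productivity) and out-of-pocket costs". The section on Health and Service Use and Productivity level, under Assessment Information, makes the same commitment. In both, resources used are multiplied by unit prices from an external source. Section 11 (Secondary aims) lists service costs as a secondary outcome and gives a self-reported questionnaire at follow-up as their source.

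That questionnaire is Section 17 of Form F in Appendix C, headed "Section 17. Health Service Use (3, 6, 9 and 12 months".

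- **GP visits.** There is a cumulative item, "17.1.1. If Yes, how often since your TIA/stroke", and an interval item, "17.2. Have you visited your GP since the last assessment", followed by "17.2.1. If Yes, how frequently have you visited your GP". Both counts offer one, two, three, four, then "More than 4 times", plus an option for not remembering. Neither has a count field.
- **Private care.** Item 17.14 asks yes or no about paying at present. The only follow-up is "17.14.1. If Yes to 17.14, what services".
- **Timing.** In Table 1 (Section 20) the row "Health and Service costs: NMDS (NZ" is ticked at 6 and 12 months only. The table has no 9-month column. The list of case record forms assigns Form F to 3, 6, 9 and 12 months, and Section 18 (Assessments) schedules contacts at all four.

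**The concern.** An analysis plan can choose how to price and model resource use, but it cannot recover quantities the form never asked for. Out-of-pocket cost is promised by name. Yet the one item on privately paid care gives neither a number of visits to multiply by a unit price nor an amount that could be used directly. Because it asks about paying at present, a service bought and finished between two contacts can also be missed.

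The GP cap is a smaller fault of the same kind: anyone with five or more visits in a recall window is recorded identically. The timing disagreement matters because the interval item works only if it is asked at every assessment.

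At stake are a secondary outcome and the cost side of the incremental cost per QALY. The primary endpoint, systolic blood pressure at 6 months, is unaffected.

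**Working it through.** The protocol states no figure to reproduce, so the check has three parts.

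**1. Promise against field (private care).** Costing needs either quantity × unit price or an amount paid. Item 17.14 gives current status; item 17.14.1 gives type of service. Visits, duration and amount are all absent. External unit prices can replace the missing amount, but nothing replaces the missing quantity.

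**2. Size of the GP cap.** The documents give no visit rate, so all rates here are assumptions. Let X be the number of visits in a recall window, Poisson with mean m = annual rate × window/12, with the top category coded as 5.

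- Recorded mean: E[min(X,5)] = P(X≥1) + P(X≥2) + P(X≥3) + P(X≥4) + P(X≥5)
- Share of visits lost: 1 − E[min(X,5)]/m

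Example: 8 visits a year over 3 months gives m = 2. Then E[min(X,5)] = 1.978, and the loss is 1 − 1.978/2 = 1.1%.

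| Assumed visits a year | P(X>4), 3 months | Lost, 3 months | Lost, 6 months | Lost, cumulative item at 12 months |
|---|---|---|---|---|
| 4 | 0.4% | 0.1% | 1.1% | 10.3% |
| 8 | 5.3% | 1.1% | 10.3% | 39.5% |
| 12 | 18.5% | 4.5% | 25.3% | 58.4% |
| 16 | 37.1% | 10.3% | 39.5% | 68.8% |

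The 3-month column applies to the interval item on Form F's schedule. The last column applies only if the cumulative item were used alone, with its window taken as 12 months.

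Effect on a between-arm difference with quarterly recall, assuming means of 2.0 and 2.5 per window:

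- Poisson: recorded means are 1.978 and 2.438. The difference of 0.50 becomes 0.46, a loss of about 8%.
- Clustered visits (negative binomial, dispersion 1): with q = m/(1+m), P(X>4) = q⁵ and E[min(X,5)] = m(1 − q⁵). For m = 2.0, q⁵ = 0.132 and the recorded mean is 1.74. For m = 2.5, q⁵ = 0.186 and it is 2.04. The difference of 0.50 becomes 0.30, a loss of 40%.

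**3. Months covered by item 17.2.** Assessments are at 0, 3, 6, 9 and 12 months, so each answer covers the preceding 3 months.

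- Asked at 3, 6, 9 and 12 months (Form F): 4 × 3 = 12 of 12 months.
- Asked at 6 and 12 only (Table 1), with the 3- and 9-month contacts still held: 2 × 3 = 6 of 12 months, missing months 0–3 and 6–9.

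**The case against.** The strongest reply is that little is lost in practice. Banded answers are a common compromise in telephone recall. An open top category can be given a value and varied, and the protocol plans sensitivity and probabilistic analyses. With quarterly recall the Poisson loss is about 1% of visits even at 8 a year. Hospital admissions are captured separately on Form S. Unit prices come from outside, so a missing dollar amount is not in itself a flaw. All of this stands, and it keeps the GP point modest. It does not supply the missing quantity for private care.

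A reader might draw four stronger conclusions, which the documents do not support:

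- **Half the year is unobserved.** Section 17 and the form list both say 3, 6, 9 and 12 months, which gives contiguous windows. Items 17.1 and 17.3 also ask about the whole period since the event. The Table 1 row carries an NMDS label and may describe another source.
- **Most of a between-arm difference vanishes.** With 6 versus 7 visits on the cumulative item, the recorded means are 4.48 and 4.71, so a difference of 1.0 becomes 0.23, a loss of about 77%. That needs the 12-month cumulative item to be used alone, and nothing says it will be.
- **The cap flatters coaching.** The session outline mentions referrals, but the economic section expects resource savings. Neither shows which arm will see its GP more.
- **Out-of-pocket cost cannot be estimated at all.** Status and type are recorded, so a figure could be built on assumed quantities. It would not rest on collected ones.

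**Conclusion.** The point holds in a limited form. The firmest part is privately paid care: the protocol promises an out-of-pocket component, and the form collects no quantity, duration or amount for it. The GP cap is real, and its size depends on rates the documents do not give. It is about 0.1% to 10% of visits with quarterly recall under assumed Poisson rates of 4 to 16 a year and top category coded 5, and more with clustered visits or reliance on the cumulative item. Any effect on the between-arm comparison has unknown direction.

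The timing issue is a contradiction to reconcile rather than a demonstrated gap. Item 17.2 misses months only if Table 1 governs Section 17. Together these weaken a listed secondary outcome and justify a change to the form.

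**What to change.** 1. Make items 17.1.1 and 17.2.1 whole-number fields, keeping an option for not remembering.
2. Add to item 17.14.1, for each service named, the number of visits and the amount paid since the previous assessment.
3. Align the Table 1 service-cost row with Form F at 3, 6, 9 and 12 months, adding the missing 9-month column, and state which data come from NMDS and which from self-report.

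Section 17 is also printed in Form B, so both copies should match. The cost is a few REDCap field changes, a table correction and a slightly longer call, with no extra contacts. Answers already collected in the present format could not be upgraded, so the change is worth most if made early.

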17.3. Have you received other healthcare services since your stroke/TIA?  Yes  No

17.3.1. Which services have you received?  visiting nurses  
 speech therapy  
 psychologist  
 physiotherapy  
 social worker  
 counsellor  
 occupational therapist  
 other health provider (e.g. neurologist)  
 other

17.4.1. For the above services, how many visits did you receive per week?  1  2  3  4  
 5 or more

17.4.2. For the above services, how many visits did you receive per week?  1  2  3  4  
 5 or more

17.4.3. For the above services, how many visits did you receive per week?  1  2  3  4  
 5 or more

17.4.4. For the above services, how many visits did you receive per week?  1  2  3  4  
 5 or more

17.4.5. For the above services, how many visits did you receive per week?  1  2  3  4  
 5 or more

17.4.6. For the above services, how many visits did you receive per week?  1  2  3  4  
 5 or more

17.4.7. For the above services, how many visits did you receive per week?  1  2  3  4  
 5 or more

---

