### DATA COLLECTION AND FOLLOW-UP

Research assistants (RAs) will be provided training and ongoing supervision to conduct assessments. All assessments will be conducted in a standardised manner in accordance the Protocol. The Project Manager will conduct the randomisation and assign cases to the RAs. RAs will be blinded to the treatment group.

---

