17.7 State what other services you have received

---

---

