17.10.1 Do you receive any other type of help?

- Yes    No

---

17.11.2. State what other help you receive.

---

---

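### Form F's service-use questions do not exclude study contacts, so coached participants may reveal their allocation to blinded assessors, and coaching could be counted twice in the costs

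*Protocol*

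**What the plan says.** **The form.** Section 17 of Form F, on health service use, is headed for all four follow-ups. After the GP items, 17.3 asks "Have you received other healthcare services since your stroke/TIA". The options in 17.3.1 include psychologist, counsellor, other health provider and other, and 17.4 asks for the number of visits per week. Item 17.7 is free text: "State what other services you have received". After the home-help items, 17.10.1 asks "Do you receive any other type of help", and 17.11.2 continues "State what other help you receive". No item or note in the section excludes contacts that are part of the trial.

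**Blinding.** Data Collection and Follow-up states that "RAs will be blinded to the treatment group". Section 29 makes the 3-month assessment telephone only and takes the primary outcome in person at 6 months. Appendix A provides a reminder sheet so that participants do not reveal HWC membership, but lists it among the requirements for a face-to-face visit. No telephone equivalent is stated.

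**Coaching.** Section 27 sets 12 sessions over 6 months (4 weekly, 6 fortnightly, 2 monthly), then short monthly calls until the 12-month assessment. The Usual Care section says usual-care (UC) participants are not told about the coaching.

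**Costs.** The secondary outcomes in section 11 take service costs from a self-reported questionnaire. Table 1 names NMDS as the source and ticks 6 and 12 months. The Health Economic Evaluation separately deducts Program Costs, defined as "non-research related costs associated with providing the intervention".

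**The concern.** The trial is open-label with a blinded end-point, so the assessors' ignorance of allocation is its main protection against measurement bias. A scripted question that a coached participant could truthfully answer by naming the coach works against that protection, and only one arm has such an answer to give. If it happens at 3 months, it precedes the primary blood pressure reading, and no later analysis can restore the blinding. The assessor-administered secondary measures, such as the MoCA and HADS, are exposed too.

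On cost, the intervention already has its own place in the evaluation. Any coaching that also enters through Section 17 would be charged again, in the HWC arm only, which would bias the cost comparison against HWC.

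**Working it through.** The plan states no figure on this point, so there is none to reproduce. The check is a count of contacts and a comparison of the relevant texts.

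**1. Coaching delivered before the 3-month call.** Inputs: the schedule in section 27 and the 3-month window of plus or minus 2 weeks in section 29. Assumption: the first session is in week 1 after randomisation.

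- Weekly sessions: weeks 1, 2, 3, 4
- Fortnightly sessions: weeks 6, 8, 10, 12, 14, 16
- Monthly sessions: about weeks 20 and 24

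| Timing of call | Sessions by then |
|---|---|
| Week 11 (early) | 4 + 3 = 7 |
| Week 13 (nominal) | 4 + 4 = 8 |
| Week 15 (late) | 4 + 5 = 9 |

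Participants are therefore in active coaching when first asked. The first two sessions and the last are face to face, so of the 8 by week 13, 2 are in person and 6 by telephone.

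**2. Is Section 17 due at 3 months?** The Form F heading and the form list in Appendix C both say so. Table 1 ticks service costs only at 6 and 12 months. But Table 1 also ticks productivity at 3 months, and the employment items (17.12 to 17.13) sit inside Section 17. The texts conflict, but Table 1 does not remove the section from the 3-month call.

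**3. The route to double costing.** Let S be service cost by arm, P the programme cost, and x the cost of any coaching recorded and priced in Section 17.

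- Intended net saving: (S_UC − S_HWC) − P
- With coaching also in Section 17: (S_UC − (S_HWC + x)) − P
- Error: −x, where x is zero or more

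The lower bound is zero: nobody reports coaching, or such entries are removed before pricing. In delivered contacts, the most that could be counted again is 12 sessions plus about 6 monthly calls, or about 18 per HWC participant. The documents give no price for these contacts, so x has no supportable money value.

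**4. How the form would record it.** The lowest frequency in 17.4 is 1 visit per week. Applied over 13 weeks, that implies 13 visits against about 8 sessions delivered, so coaching reported there would be overstated as well as duplicated.

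**5. Could the data be cleaned?** A free-text entry naming a study coach can be recognised and removed. A tick against 'counsellor' has no identifying text and cannot be told from outside counselling.

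**The case against.** **Participants may not class coaching as a health service.** The list in 17.3.1 is mostly clinical, the open help item follows questions on home help, and coaches are trained to distinguish coaching from counselling and psychotherapy. Most sessions are telephone calls, which are not obviously visits. All this lowers the likely frequency. It does not close the route, because 'other' and the free-text items remain open.

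**Blinding is already addressed.** The randomisation form is hidden from research assistants and a reminder sheet exists. It may be used at the face-to-face baseline visit, before the 3-month call. But at baseline the participant has no allocation to disclose, and a general reminder is weak against a later direct question. Appendix A refers to a Manual of Procedures, which is not shown and may contain telephone wording; that uncertainty stands.

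**The effect on the primary outcome is indirect.** No text says that the same assistant makes the 3-month call and takes the 6-month reading; assignment of cases to assistants only suggests it. Blood pressure is the average of three readings on an automatic monitor, which limits assessor influence. Both points stand.

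**Costing rules may sit in an analysis plan.** Pricing and cleaning can be settled there, but the wording put to the participant cannot.

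**Stronger readings.** A reader might infer that coaching is bound to be costed twice, or that participants are bound to name their coach. The documents support neither. Double costing requires coaching to be reported, recorded and priced, and none of these steps is stated. Nor do they support a total such as 12 × 180 = 2,160 duplicated sessions, a dollar amount, or a count of participants unblinded before the primary reading.

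**Conclusion.** The point holds as a risk built into the form. As written, Section 17 has blinded assessors ask about other services and help, with no exclusion of study contacts, when about 8 of 12 sessions (7 to 9 across the visit window, first session assumed in week 1) have taken place. Disclosure before the 6-month assessment is possible, and the only stated reminder is listed for face-to-face visits. Coaching could also enter service costs in addition to Program Costs, in the HWC arm only.

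The size of both effects is unknown and may be zero. Carry-over to the primary outcome further requires that the assessor who learns the allocation also takes, or influences, the 6-month reading. The change is worth making because unblinding cannot be undone and prevention costs very little. The conflict over the source and timing of service costs is a separate, definite inconsistency, and it determines whether Form F answers enter the costs at all.

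**What to change.** 1. Open Section 17 of Form F with a neutral line read to both arms, for example: please do not include or mention any contact that is part of this study. Repeat it at 17.7 and 17.11.2. The line should not mention coaching, because UC participants are not told about it.
2. Give the blinding reminder at the 3-, 9- and 12-month telephone assessments as well as at face-to-face visits.
3. In the Health Economic Evaluation, state that coaching is costed only as Program Costs, from the Form Z session records.
4. Reconcile the source and timing of service costs: Table 1 has NMDS at 6 and 12 months; the secondary outcomes and Form F rely on self-report, with Form F at 3, 6, 9 and 12 months.

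The cost is a few lines on a REDCap form, a short addition to the telephone script and two clarifications in the protocol text. Sample size, visit schedule and the primary analysis are unaffected.

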### 11. SECONDARY AIMS

The **secondary aims** are to determine the effectiveness of HWC in improving

1. Overall cardiovascular disease (including stroke) risk at 6 months post-randomisation based on the LS7 compared to Baseline

2. Individual LS7 behavioural risk factors at 3-, 6- 9- and 12- months post-randomisation compared to Baseline
3. Awareness about stroke symptoms, risk factors and their management 6- and 12- months post-randomisation compared to Baseline
4. Quality of life, at 6- and 12- months post-randomisation compared to Baseline
5. Cognitive outcomes at 6-, and 12- months post-randomisation compared to Baseline
6. Mood outcomes compared to Baseline
7. Adherence to CVD medications at 3, 6-, and 9 and 12- months compared to Baseline
8. CVD/adverse outcomes at 12 months post randomisation.
9. Health and service costs at 12 months post randomisation
10. Productivity status at 12 months post randomisation

Secondary outcomes are:

1. systolic blood pressure, total cholesterol, blood glucose at 6-months post randomisation
2. change in proportion of participants in 'high' and 'intermediate' to 'low' risk on LS7 at 6-months post randomisation
3. Stroke risk from Stroke Riskometer – 5- year absolute and relative risk at 6- and 12-months post randomisation
4. Quality of life (EQ5D) at 6-months post randomisation
5. Stroke awareness at 6- and 12-months post randomisation
6. Cognitive assessment score (Montreal Cognitive Assessment)
7. Medication adherence (Self-Efficacy For Appropriate Medication Use Scale (SEAMS))
8. CVD adverse outcomes (fatal and nonfatal stroke, TIA, myocardial infarction and heart failure, death attributable to CVD and all-cause mortality)
9. Healthcare and community service costs assessed as self-reported service use questionnaire at follow up. Productivity status will be self-reported and will include items regarding status (e.g., paid work, voluntary work, homemaker, student, unemployed), hours (e.g., full/part time), compared to hospitalisation pre-stroke status.

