## 24. OUTLINE OF SESSIONS

Topic	Aims/Strategies for the first session (in-person)
Session opening	Introductions, setting expectations, discussing the study and confidentiality, setting agenda
Health risk assessment	Focus on positive and strengths, values and readiness to change for participant, make appropriate referrals
Wellness vision	Dreams and vision of self and wellbeing in 3-5 years, identify values and motivators
Three month goals	Mid-term goals for consistent behaviours to be doing in three months' time, consider barriers and supports
Weekly goal(s)	First experiment and short-term step forward in an area that the participant is motivated and ready to change
Session close	Affirm belief in the participant and their autonomy, review how the process can be improved, schedule next session
Topic	Aims/Strategies for the first session (over the telephone or in-person, if required)

Session opening	Check in, highlight of the week, set the agenda
Review weekly goals	Focus on positive, explore full experience, reflect participant's strengths and values. Review vision and three month goals. Confirm the vision and three month goals are still where the client is heading, only done once per month
General moment	Participant identifies a target behaviour to address, explore ideal situation, best past experience, values and strengths, and brainstorm ideas
Set weekly goals	Next step in behaviour change in an area the participant is motivated and ready to change, SMART (Specific, Measurable, Action-based, Realistic and Time-bound) goals
Session close	Affirm belief in the participant and their autonomy, review how the process can be improved, schedule next session (if relevant)

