17.5. Have you received other healthcare services since the last assessment ?

- Yes    No

---

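### Form F records nurse, therapy and specialist visits only as a weekly rate, with no less-than-weekly option and no duration, so total visits for the self-reported cost endpoint cannot be derived

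*Protocol*

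**What the plan says.** Section 11 (Secondary aims, outcome 9) sets the source of the cost outcome: "Healthcare and community service costs assessed as self-reported service use questionnaire at follow up". Section 31 lists health service use and costs among the secondary end points. Section 34 plans a comparison of service utilisation costs between arms. The Health Economic Evaluation section builds direct costs and an incremental cost per QALY on resource use. Table 1 also names the NMDS against health and service costs, at 6 and 12 months.

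The questionnaire is Section 17 of Form F, headed for the 3-, 6-, 9- and 12-month assessments. The same section is printed in Form B.

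- **Lead-in for services other than the GP:** "17.3. Have you received other healthcare services since your stroke/TIA", followed by a tick list (17.3.1) of nine service types.
- **Quantity:** items 17.4.1 to 17.4.9, each worded as "17.4.1. For the above services, how many visits did you receive per week", with options 1, 2, 3, 4 and 5 or more.
- **Interval items:** "17.5. Have you received other healthcare services since the last assessment" (yes/no), repeated almost word for word as 17.6. Items 17.5.1 and 17.7 take free text on the type of service.
- **GP visits:** "17.2. Have you visited your GP since the last assessment", with a parallel item on the period since the event. Each has a count from one to four and an open category above four.
- **Home help (17.9.2):** a frequency scale that reaches fortnightly and monthly or less.

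**The concern.** To cost a service one needs the number of contacts. A weekly rate gives that number only when multiplied by the number of weeks, and Form F does not ask for weeks, start dates or stop dates. The scale also assumes that everyone who used a service used it at least weekly. That assumption does not fit several services on the list, most plainly the specialist category, for which a single consultation is an obvious pattern of use.

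At stake is the community and specialist part of a named secondary outcome and of the economic evaluation. This is a fault of data collection, so no analysis plan can recover a duration that was never recorded.

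**Working it through.** The protocol gives no visit counts, unit costs or conversion rule, so there is no planned figure to reproduce. The check has two parts: what the form can identify, and an illustration of how far one answer can be from the truth.

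**1. What the form identifies**

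Total visits to a service = visits per week × weeks of use.

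| Item | Window | Quantity obtained | Less-than-weekly use recordable? |
|---|---|---|---|
| 17.1.1, 17.2.1 GP | since event; since last assessment | number, 1 to 4, then open | yes |
| 17.9.2 home help | follows an item on the last interval | frequency scale | yes |
| 17.3, 17.3.1 other services | since event | yes/no and type | not applicable |
| 17.4.1–17.4.9 other services | none stated; follows 17.3 | visits per week, 1 to 5 or more | no |
| 17.5, 17.6 other services | since last assessment | yes/no | not applicable |
| 17.5.1, 17.7 other services | follow the items above | free text on type | not applicable |

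For the nine services under 17.3.1, the first factor is measured on a scale that starts at 1 and is open at the top. The second factor is not measured at all. The GP and home-help items show that the form's authors had workable formats available.

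**2. Illustration (assumed conversion)**

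Assume a 13-week window: 3 months × 365.25 / 12 / 7 = 13.0 weeks. Counted from the event, the window could be up to 6 weeks longer, because Section 29 allows baseline up to 6 weeks after the index event. Assume also that the analyst multiplies the ticked rate by the whole window.

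- One consultation, ticked as 1 per week: 1 × 13 = 13 recorded against 1 real.
- One consultation, item left blank: 0 recorded against 1 real.
- Two visits, ticked as 1 per week: 13 / 2 = 6.5 times the true number.
- Three visits, ticked as 1 per week: 13 / 3 = 4.3 times.
- A course of six weekly sessions, answered correctly as 1 per week: 13 / 6 = 2.2 times.

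The last line matters because the respondent has made no mistake. A tick of 1 fits any total from 1 to 13 in that window, and nothing else on the form narrows it.

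**3. After the change proposed below**

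One consultation counts as 1 and a course of six counts as 6. No change in the cost endpoint itself can be computed, because the protocol gives neither visit rates nor unit costs.

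**The case against.** **What stands on the other side.** The affected block is limited. GP visits have their own counts, home help has a usable scale, admissions are recorded on Form S, and the NMDS is named as a further source for costs. The proportion of participants using each service can still be read from 17.3 and 17.3.1. The handling of answers may be set out in an analysis or health-economics plan that is not at hand. All of this is fair and keeps the point away from the primary endpoint. It does not supply the missing duration, and the protocol does not say that the NMDS will provide visit counts for these services.

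**Stronger readings that the document does not support.**

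- *Costs will be inflated 13-fold or more.* This presumes that the rate is multiplied over the whole window, and no such rule is stated. A participant with one visit may leave the item blank, which gives an undercount. The direction is unknown.
- *Repeated since-event answers count the same care several times.* Adding windows of 13, 26, 39 and 52 weeks gives 130 weeks against 52, or 2.5-fold. That needs 17.3 and 17.4 to appear at every follow-up, each rate to be multiplied by its full window, and the four results to be added. Appendix C is a flat print of the database fields. It does not show which items appear at which visit, and it prints Section 17 even in the baseline form. No analysis of that kind is planned anywhere.
- *The error will favour one arm.* The outline of the first coaching session includes "values and readiness to change for participant, make appropriate referrals", so extra one-off visits in the coaching arm are conceivable. The protocol gives no referral numbers and does not link referrals to the services in 17.3.1. Both arms use the same form. Differential bias is possible but not shown.

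**Conclusion.** The point holds in a limited form. For the nine service types under 17.3.1, total visits cannot be derived from Form F as written, and use below once a week has no correct answer. This makes the community and specialist part of the self-reported cost outcome, and of the economic evaluation that draws on it, unreliable by an amount and in a direction that depend on how answers are given and converted. In the 13-week illustration a single visit may count as anything from 0 to 13.

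The conclusion about what cannot be derived rests only on the printed items. The 0-to-13 range rests on the assumed window and conversion. The primary blood pressure endpoint and the Form S admissions data are not touched. GP visits lose information only above four. The form should be corrected, but the fault does not threaten the trial's main result.

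**What to change.** On Form F:

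1. Replace 17.4.1 to 17.4.9 with one numeric field per service for the total number of visits, 0 allowed, each labelled with its service.
2. Set the window by visit: since the stroke or TIA on the 3-month form, and since the last assessment at 6, 9 and 12 months.
3. Keep one lead-in item on services since the last assessment and delete its duplicate (17.5 or 17.6).
4. Make the GP count numeric, without the open category above four.
5. Make the copy of Section 17 in Form B agree with the revised section.

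The cost is a small REDCap edit. Data already collected on the old items cannot be repaired. They would need a sensitivity analysis that treats a weekly tick, and a blank for a service ticked in 17.3.1, under both low and high assumptions about the number of visits.
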